Enrollment is expected to take up to 4 months to achieve the proposed sample size. Subjects will be followed for 3 months after hospital discharge. Data collection will occur in real-time throughout the study, and final data analysis will be performed at conclusion of the study.

Section II: Design

Background & Significance

Early IV to PO antimicrobial transition for serious infections including endocarditis and bone and joint infections is noninferior to prolonged IV antimicrobial therapy; this is supported by landmark studies published in the New England Journal of Medicine.^{1,2,3} As compared to inpatient IV antimicrobial therapy, OPAT has a similar adverse event rate but results in substantial cost savings.⁴ Challenges with IV antimicrobial therapy include vascular access requirement and risk of associated complications (i.e. bacteremia/fungemia and deep venous thrombosis) and social circumstance limitations.⁵ COpAT uses PO antimicrobials with high bioavailability in place of IV antimicrobials.^{5,6} According to retrospective data, early IV to PO antimicrobial transition compared to prolonged IV antimicrobial therapy for endocarditis has similar outcomes with fewer adverse events.⁷ Our early experience at WVUH suggests COpAT is not only clinically effective and safer but also results in significant additional cost savings.⁶ However, unlike OPAT, COpAT programs are not yet widely incorporated into clinical practice. In addition, clinical trials evaluating safety superiority with equivalent effectiveness of early IV to PO antimicrobial transition across various infectious diseases are lacking.

The COPAT Trial is designed to demonstrate equivalent effectiveness with improved safety of early transition from IV antimicrobial therapy to COpAT across various infectious diseases (endovascular, bone and joint, skin and soft tissue, pulmonary, gastrointestinal, and genitourinary infections); we hypothesize that adverse events will be significantly reduced in patients discharged from the hospital with COpAT versus standard of care with no significant difference in efficacy between groups. Should results of the COpAT Trial support the hypothesis, the evidence may promote more widespread incorporation of COpAT programs into clinical practice, improving patient care and resulting in lower cost of care.

Objectives

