Purpose: To demonstrate improved safety and equivalent effectiveness of early transition from IV antimicrobial therapy to COpAT across various infectious diseases (endovascular, bone and joint, skin and soft tissue, pulmonary, gastrointestinal, and genitourinary infections)

Primary Outcomes: Cure at 3 months using clinical (resolution of infection) and laboratory (improvement in inflammatory markers) parameters during ID Clinic follow-up as adjudicated by a 2-person evaluation team of ID faculty on the research team blinded to study arm and adverse events related to antimicrobial therapy/vascular access complication or readmission at 3 months.

Secondary Outcome: Patient satisfaction using a patient satisfaction survey (separate attachment) administered at 6-week ID Clinic follow-up.

Rationale: Key focuses of this study are safety, effectiveness, and implementation science.

- **Safety:** This study will evaluate safety superiority with early transition from IV antimicrobial therapy to COpAT versus standard of care antimicrobial therapy across various infectious diseases.
- **Effectiveness:** This study will evaluate effectiveness equivalence between early transition from IV antimicrobial therapy to COpAT and standard of care antimicrobial therapy across various infectious diseases.

- **Implementation Science:** Conducting this study will promote development of COpAT programs at additional WVU Medicine institutions. Should this study prove our hypothesis, COpAT programs will be more widely incorporated into clinical practice.

Study Design & Methodology

This is an investigator initiated multisite pragmatic randomized controlled trial designed to demonstrate equivalent effectiveness with improved safety of early transition from IV antimicrobial therapy to COpAT across various infectious diseases (endovascular, bone and joint, skin and soft tissue, pulmonary, gastrointestinal, and genitourinary infections). Primary and secondary outcome data will be collected prospectively.

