If an infection is not improving or a patient is having major side effects, treatment may be changed to IV antibiotics (if a patient is receiving oral) or oral antibiotics (if a patient is receiving IV).

Benefit: Patients may be discharged from the hospital sooner and have a reduced risk of adverse events related to vascular access device if randomized to the experimental group.

Statistical Analysis Plan

Sample Size: As the hypothesis is that adverse events will be significantly reduced in the experimental group with no significant difference in efficacy between groups, 135 patients (*Experimental*: 90 patients; *Control*: 45 patients) are needed to have power greater than 80%. Calculations were performed through consultation with a biostatistician using failure and adverse event rates for COpAT/PO antimicrobial therapy taken from data presented and published on 100 patients who completed the WVUH COpAT Program and for conventional/intravenous antimicrobial therapy taken from clinical trial data published on serious infections including endocarditis and bone and joint infections.

Sample Size Allocation: As the study will be conducted across 5 WVU Medicine hospitals, the number of subjects each site expects to enroll is as follows: J.W. Ruby Memorial Hospital 90 patients, United Hospital Center 18 patients, Berkeley Medical Center 12 patients, Wheeling Hospital 9 patients, Camden Clark Medical Center 6 patients.

Data Safety Monitoring: A Data and Safety Monitoring Plan will be implemented to facilitate ongoing review of the study, actions, data collection, and analysis throughout the entirety of the project. It will include details regarding handling serious adverse events (SAEs)/adverse events (AEs). A Data Safety Monitoring Board (DSMB) has been formed to oversee subject safety including one member not on the research team who is an expert in the field of ID: [name], MPH, FSHEA, FIDSA, FACP, WVU Health System's System Healthcare Epidemiologist and Associate Chief Quality Officer for Infection Prevention and Antimicrobial Stewardship and WVU Professor of Internal Medicine and Public Health, accepted his nomination to serve this role. The DSMB will review data and provide monitoring at 3 points in the study: after 45 patients are enrolled, after 90 patients are enrolled, and after 135 patients are enrolled.

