Early Stopping and Selection: Bayesian statistical model will be used to assess efficacy outcomes and adverse events in the interim analysis. In particular, the predictive probability (for the final sample size) of primary outcomes will be estimated, given the current data. Denoting the posterior probabilities of adverse event outcome p_1 (Control Arm) and p_2 (Experimental Arm), respectively; the posterior probabilities of efficacy outcome by q_1 (Control Arm) and q_2 (Experimental Arm), respectively.

If $\text{Prob}\{p_1 > p_2 \mid \text{data}\} > 0.90$ and $\text{Prob}\{ |q_1 - q_2| < 0.10 \mid \text{data}\} > 0.90$,
then the trial will be stopped early, and the experimental arm will be selected as superior arm.

Safety Monitoring & Unanticipated Event Reporting

In addition to the DSMB, the principal investigators will be responsible for data quality management and safety monitoring. At hospitals other than J.W. Ruby Memorial Hospital, site co-investigators will provide enrollment reports

WVU+kc Protocol #: 2304754420

PIs: [name], and [name], MSc, MBA

to the principal investigators weekly and report any serious events to the principal investigators immediately. The principal investigators will then report any adverse or unanticipated events to the IRB in conjunction with requirements outlined by the IRB. The principal investigators will chair a monthly meeting including collaborating site co-investigators to ensure all data entry for current subjects is complete and up to date, review safety data including all serious events, and discuss all protocol deviations.

Study Duration & Timeline

Study Duration:

Enrollment is expected to take 4 months to achieve our proposed sample size. Subjects will be followed for 3 months after hospital discharge. Data collection will occur in real-time throughout the study, and final data analysis will be performed at conclusion of the study.

Section III: Informed Consent Process

Protected Health Information (PHI)

Our study will require dealing with PHI, including names, medical record numbers, dates, and phone numbers. PHI will not be used for data analysis or reported/published. All PHI will be kept confidential.

Informed Consent Process

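### The aim is equivalent cure, but the hypothesis is worded as no significant difference, and the only equivalence criterion (margin 0.10) is written for the interim stopping rule

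*Combined protocol and SAP*

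**What the plan says.** **Aim.** Background & Significance describes the trial as "designed to demonstrate equivalent effectiveness with improved safety". The Rationale under Objectives adds: "This study will evaluate effectiveness equivalence between early transition from IV antimicrobial therapy to COpAT and standard of care antimicrobial therapy". Cure at 3 months is one of the primary outcomes.

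**Hypothesis.** The Sample Size paragraph of the Statistical Analysis Plan reads "As the hypothesis is that adverse events will be significantly reduced in the experimental group with no significant difference in efficacy between groups", and derives 135 patients (90 experimental, 45 control) and power above 80% from it. The phrase "with no significant difference in efficacy between groups" also stands in the Research Summary (Study Population), in Background & Significance, and in Target Population & Recruitment Methods (Sample Size).

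**Criterion.** The only margin is under Early Stopping and Selection, introduced by "Bayesian statistical model will be used to assess efficacy outcomes and adverse events in the interim analysis". If Prob{p1 > p2 | data} > 0.90 for adverse events and Prob{|q1 − q2| < 0.10 | data} > 0.90 for cure, "then the trial will be stopped early, and the experimental arm will be selected as superior arm". The same paragraph mentions a predictive probability for the final sample size.

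**Looks and final analysis.** The monitoring board reviews data "after 45 patients are enrolled, after 90 patients are enrolled, and after 135 patients are enrolled". The final analysis is said only to take place at the end of the study. No test, interval, margin, prior, error level or decision rule is attached to it.

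**The concern.** The documents make two different statements about cure. Equivalence is a positive claim that the difference lies inside a margin. A non-significant difference means only that the data did not exclude zero, and with 45 controls that can easily happen when the arms truly differ. The plan contains a criterion of the right kind, but ties it to stopping early and says nothing about a trial that runs to its end without meeting it.

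With the final criterion unwritten, the choice between a p-value and the margin could be made after the results are known. This concerns a primary outcome in serious infections, in a trial meant to change practice. The two readings can give opposite answers on the same data.

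**Working it through.** **1. The plan's own figure.** The 135 cannot be reproduced uniquely, because alpha, sidedness, cure rates and adverse-event rates are not stated. It fits more than one set of inputs:
- Adverse events of 30% v 10% (two-sided 5%, 80% power, 2:1) need 44 controls.
- Non-inferiority of cure at 95% in both arms (margin 0.10, one-sided 5%) gives controls = (1.645 + 0.842)² × 0.95 × 0.05 × (1 + 1/2) / 0.10² = 44.1. This rounds up to 45, or 135 in total.

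So 135 is neither confirmed nor refuted, and the text does not say which outcome the power belongs to.

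**2. Inputs for the comparison.**
- From the documents: 90 v 45, margin 0.10, threshold 0.90.
- Assumed: control cure 97/95/90/85%, flat Beta(1,1) priors, a two-sided 5% chi-square test, one final look, and complete outcomes. Only the cure half of the stopping rule is evaluated.

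**3. Method.** With x1 of 45 and x2 of 90 cured, the posteriors are q1 ~ Beta(1 + x1, 46 − x1) and q2 ~ Beta(1 + x2, 91 − x2). For each of the 91 × 46 possible tables, compute the chi-square p-value and Prob{|q1 − q2| < 0.10}. Then sum the binomial probabilities of the tables in each category.

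**4. True 10-point COpAT deficit.**

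| Control v COpAT cure | Non-significant | Plan's criterion met | Non-significant, criterion not met |
|---|---|---|---|
| 97% v 87% | 53.9% | 12.2% | 41.7% |
| 95% v 85% | 60.6% | 8.1% | 52.5% |
| 90% v 80% | 70.2% | 1.2% | 69.0% |
| 85% v 75% | 75.2% | 0.0% | 75.1% |

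Fisher's exact test is non-significant in 61.6/66.5/72.8/77.2%.

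**5. Truly equal cure, same method.**

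| Cure in both arms | Plan's criterion met | Non-significant, criterion not met |
|---|---|---|
| 97% | 86% | 10% |
| 95% | 73% | 23% |
| 90% | 35% | 61% |
| 85% | 6% | 89% |

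**6. One concrete table.** Take COpAT 75/90 (83.3%) v control 42/45 (93.3%).
- Pooled cure is 117/135 = 0.867.
- Standard error = √(0.867 × 0.133 × (1/90 + 1/45)) = 0.062.
- z = −0.100/0.062 = −1.61, so p = 0.11 (Fisher 0.18).
- The 95% Newcombe interval is −20.0 to +2.8 points.
- Prob{|q1 − q2| < 0.10} = 0.57.

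The result is non-significant, yet far from the plan's threshold of 0.90.

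**7. The look after 135 enrolled.** The plan states: "Enrollment is expected to take 4 months to achieve our proposed sample size. Subjects will be followed for 3 months after hospital discharge". With even accrual (assumed), 135 × (4 − 3)/4 = 33.75, so about 34 patients have a 3-month outcome at that look. If all 34 were cured, Prob{|q1 − q2| < 0.10} would be:

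| COpAT v control | Beta(1,1) | Beta(0.5,0.5) |
|---|---|---|
| 23 v 11 | 0.79 | 0.89 |
| 22 v 12 | 0.81 | 0.902 |

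Whether the rule could be met on those outcomes therefore turns on the prior, which the plan does not state.

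**The case against.** The best defence is that the plan's one written decision rule is sound in kind: a two-sided margin and a posterior probability. The section title covers selection as well as stopping, the paragraph refers to the final sample size, and there is a look at the full 135. The sponsor may well have meant the rule to carry through, and the hypothesis phrase may be loose drafting in summary and sample-size sentences. That is a fair reading. But the text does not state it, and it gives no conclusion for the case where the rule is not met.

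A reader might infer three stronger things that the documents do not support.
- *That equivalence will be declared from a non-significant p-value.* No section says so. The wording only leaves room for it.
- *That the look at 135 cannot serve as the final test.* This depends on assumed accrual and on the unstated prior. With Beta(0.5,0.5), 22 v 12 all cured gives 0.902, and slower accrual would leave more completed outcomes. What stands is that the look is timed by enrolment, so few 3-month outcomes may be available.
- *That the 42 to 75% in the last column of step 4 measures hidden harm.* The same combination occurs in 10/23/61/89% of trials with equal cure. At 90% cure or lower it mostly reflects the small sample.

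It can also be objected that adopting the interim margin and threshold for the final analysis is one choice among several. That is right, so the fix leaves a stricter alternative open.

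**Conclusion.** The concern holds. The aim is equivalence, the hypothesis is absence of a significant difference, and the only equivalence criterion is written for an interim action. Under the stated assumptions, a true deficit as large as the plan's own margin would be non-significant in 54 to 75% of trials, while the plan's criterion would be met in 12% at most. Whether the arms differ by 10 points or not at all, a non-significant result does not establish equivalence.

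The percentages rest on assumed cure rates, flat priors and a single final look; earlier looks are not modelled. The mismatch in the text depends on none of these. A reader might also infer that 135 is the wrong sample size. That is not shown, because the documents do not give the rates behind it.

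**What to change.** In all four places, replace "with no significant difference in efficacy between groups" with equivalent cure, meaning a difference within the plan's own 10 percentage points. The places are the Research Summary, Background & Significance, Target Population & Recruitment Methods, and the Statistical Analysis Plan.

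Add to the Statistical Analysis Plan:

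> At the final analysis, on completed 3-month follow-up, equivalence of cure is concluded only if Prob{|q1 − q2| < 0.10 | data} > 0.90 under the stated prior. Otherwise the report states that equivalence was not shown and gives the difference with its interval. A non-significant p-value is not taken as evidence of equivalence.

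If the sponsor prefers a stricter rule, a 90% confidence interval wholly within ±10 points would serve, provided it is chosen before results are seen. Also give the cure rates for which power above 80% applies to this criterion, or limit the power statement to the outcome it was calculated for.

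**Cost.** Wording changes in the protocol and the SAP; no new patients, visits or data. The real price is that the equivalence aim may go unmet at 135. With truly equal cure of 97/95/90/85%, the posterior rule is met in about 86/73/35/6% of trials (flat priors) and the interval rule (Newcombe) in 68/48/14/2%. Power for equivalence passes 80% only when cure in both arms exceeds about 96.1% (posterior rule) or 98.0% (interval rule). In exchange, the interval rule accepts fewer trials with a true 10-point deficit: 5/3/0.5/0%, against 12/8/1/0% for the posterior rule.

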All patients referred for OPAT will be evaluated by the research team with respect to inclusion/exclusion criteria. If determined eligible for enrollment, patients will be approached by a study investigator who will present the COPAT Trial. If interested in participating in the study, patients will then complete informed consent with a member of the research team (study investigator or research coordinator after collaborating with a study investigator). Once informed consent is obtained, patients will be randomized 2:1 using computer software into experimental or control (standard of care) group, respectively: *Experimental:* COpAT only on hospital discharge; *Control:* Conventional OPAT, OPAT transitioned to COpAT later in outpatient setting, or long-acting parenteral lipoglycopeptides. For patients randomized into the experimental group, ≥2 ID physicians (principal investigators for all patients and, if at a participating hospital other than J.W. Ruby Memorial Hospital, also the site co-investigator) on the research team will collaborate to determine COpAT regimens. Both groups will be followed by an ID physician on the research team with in-person or telemedicine ID Clinic standard of care visits at 2, 6, and 12 weeks after hospital discharge. At the 6-week ID Clinic follow-up, patients will be asked to complete a patient satisfaction survey (separate attachment). At the 12-week ID Clinic follow-up, all patients who attend will receive compensation.

The following primary outcomes will be assessed: cure at 3 months using clinical and laboratory parameters during ID Clinic follow-up as adjudicated by a 2-person evaluation team of ID faculty blinded to study arm and adverse events related to antimicrobial therapy/vascular access complication (defined as any adverse event requiring intervention) or readmission at 3 months. The following secondary outcome will be assessed: Patient satisfaction using a patient satisfaction survey administered at 6-week ID Clinic follow-up (separate attachment). Data will be collected from patients directly as well as through patient satisfaction surveys and review of electronic medical records in Epic.

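### The flat 0.90 adverse-event threshold for early selection is falsely met in about 10% of trials per look; with the cure clause added, false selection of COpAT over three looks runs from under 1% to about 19%, depending on cure rate and prior.

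*Combined protocol and SAP*

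**What the plan says.** The Statistical Analysis Plan, under Early Stopping and Selection, says that a "Bayesian statistical model will be used to assess efficacy outcomes and adverse events in the interim analysis". The rule has two clauses joined by "and":

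- Adverse events: Prob(p1 > p2 | data) > 0.90, where p1 is control and p2 is COpAT.
- Cure: Prob(|q1 - q2| < 0.10 | data) > 0.90.

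If both hold, "then the trial will be stopped early, and the experimental arm will be selected as superior arm". The paragraph also mentions predictive probability for the final sample size, but the rule itself is written on posterior probabilities.

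Under Data Safety Monitoring, the DSMB reviews data "after 45 patients are enrolled, after 90 patients are enrolled, and after 135 patients are enrolled". Allocation is 2:1. The hypothesis in Background & Significance is that "adverse events will be significantly reduced in patients discharged from the hospital with COpAT versus standard of care". The sample size paragraph says that 135 patients "are needed to have power greater than 80" per cent.

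The documents state no prior, type I error, sidedness, adjustment for repeated looks, minimum adverse-event difference, simulated operating characteristics or final-analysis criterion.

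**The concern.** Fewer adverse events is the superiority half of the trial's claim. With weak priors, a 0.90 posterior that one rate exceeds another corresponds roughly to a one-sided p-value below 0.10. The same threshold applies at each look, so the chance of crossing it by luck grows with every review. Crossing it, together with the cure clause, ends the trial and attaches the word superior to COpAT. Readers who see that word beside a hypothesis of significantly fewer adverse events will assume a stricter standard than the rule applies.

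**Working it through.** **The plan's own figure.** N = 135 with power above 80% can be neither reproduced nor refuted, because no event rates, alpha or sidedness are given. As one illustration, 45 v 90 patients with assumed adverse-event rates of 30% v 10% give 81% power at two-sided 5%.

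**Inputs from the documents.** Both thresholds are 0.90 and the cure margin is 0.10. Looks are at 45, 90 and 135 patients. At 2:1 these are 15 v 30, 30 v 60 and 45 v 90 (control v COpAT).

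**Assumptions.** p and q are read as the arms' event and cure rates. Priors are independent Beta(1,1) (uniform) or Beta(0.5,0.5) (Jeffreys). Adverse-event rates are equal at 10-30%, cure rates are equal, adverse events and cure are independent, and outcomes are complete at each look. Each scenario used 400,000 simulated trials.

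**Step 1: adverse-event clause alone.** In normal approximation the clause is z > 1.2816. With equally spaced looks the correlations are sqrt(45/90) = 0.71, sqrt(90/135) = 0.82 and sqrt(45/135) = 0.58. The false-positive rate is 10.0% at one look, 15.3% over two and 18.7% over three. The Beta-binomial simulation gives about 10-12% per look, 16-18% over two and 19-20% over three.

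**Step 2: an example.** Take 5/30 control v 4/60 COpAT events at the second look, with uniform priors. The posteriors are Beta(6,26) and Beta(5,57).

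- Means: 6/32 = 0.1875 and 5/62 = 0.0806.
- Variances: 0.1875 x 0.8125/33 = 0.00462 and 0.0806 x 0.9194/63 = 0.00118.
- z = 0.1069/sqrt(0.00580) = 1.40, so the probability is about 0.92. The exact value is 0.931.

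The clause is met, while Fisher's two-sided p is 0.15.

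**Step 3: cure clause.** At 45 patients the most favourable result is that all are cured. With uniform priors the failure rates are then U ~ Beta(1,16) and V ~ Beta(1,31). P(U - V > 0.10) is about 0.118 and P(V - U > 0.10) about 0.012, so the clause can reach at most 1 - 0.130 = 0.870. The rule therefore cannot fire at the first look under uniform priors. Under Jeffreys priors the maximum is 0.937, so it can. With uniform priors and equal cure of 90%, the clause passes in 4% of trials at 90 patients and 35% at 135.

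**Step 4: both clauses.** Under independence, the false-selection rate at a look is the product of the two pass rates. At 135 patients with uniform priors and 20% adverse events, this is 0.346 x 0.105 = 3.6% at 90% cure and 0.727 x 0.105 = 7.6% at 95%. Accumulated over looks, with ranges covering both priors:

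| True cure, both arms | First two looks | Three looks |
|---|---|---|
| 80% | about 0% | 0.03% |
| 85% | under 0.2% | 0.6-0.7% |
| 90% | 0.5-1.7% | 4-4.5% |
| 95% | 4-7.5% | 9-12% |
| 98-99% | 8-16% | 13-19% |

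**Step 5: timing.** At uniform accrual over 4 months, 45 patients are reached at 4 x 45/135 = 1.3 months and 90 at 2.7 months. Nobody then has a 3-month outcome. At 135 patients about a quarter do (those enrolled in the first of four months).

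**The case against.** A reader might infer that the selection rule as a whole carries a 10% error at every look and 15-20% over the trial. The documents do not support that. Those figures belong to the adverse-event clause. The rule needs the cure clause too, and that clause is hard to meet at these sample sizes. The full rule reaches 15% or more only with cure near 97-99%, and there the figure depends on the prior (at 99% cure, 13-15% uniform and 18-19% Jeffreys). The documents give no cure rate.

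A reader might also infer that a trial stopped on this rule could never support a claim of significantly fewer adverse events. That presumes no separate final test. The plan schedules a final analysis without giving its criterion, and it ties the Bayesian model to the interim analysis. Whether 0.90 governs at 135 patients, which is full enrolment, is not stated, so the two-look column is shown as well.

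Two further objections stand. Complete outcomes at each look conflict with the plan's own timeline, so the table describes the rule's properties and does not forecast how often it will fire. And 2.5% is a convention that the documents do not adopt; a Bayesian design may choose another level.

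None of this removes the point. The cure clause limits how often the rule can fire but gives no further evidence on adverse events. Under independence, whenever it passes at a look, the adverse-event clause is still falsely met about 10% of the time if rates are equal. An unstated prior also decides whether the first look can stop the trial at all.

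**Conclusion.** The concern holds for the adverse-event clause, and for the full rule when cure is high. The clause is falsely met in about 10% of trials per look and 19-20% over three looks. The full rule exceeds one-sided 2.5% over three looks at 90% cure (4-4.5%) and clearly so at 95% (9-12%) and 98-99% (13-19%). At 80-85% cure it stays below 1%. If only the first two looks count, it exceeds 2.5% at 95% cure and above, but not at 90%.

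These figures rest on the priors, adverse-event rates, independence and complete data assumed above. Independence is a simplification: the safety outcome includes readmission, which may well be linked to treatment failure, and the effect of that link was not computed.

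**What to change.** In Early Stopping and Selection, replace the flat 0.90 for adverse events by higher, look-specific thresholds. Calibrate them by simulating the full two-clause rule, so that the chance of selecting COpAT when adverse-event rates are equal stays at or below a pre-stated one-sided level (2.5%, for example) over all looks and across plausible cure rates. Fix in advance the prior and the outcome data used at each look, given the accrual and follow-up times. State which criterion governs the final safety claim.

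Thresholds of 0.999/0.99/0.98 at 45/90/135 are an illustration only. With complete data they hold the adverse-event clause alone to about 2.5-2.7%, and the full rule to about 0.8% at 90% cure and 1.7-2.0% at 95%. Near 100% cure the full rule approaches the clause-alone figure, so a strict 2.5% cap would need slightly higher values.

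The work is SAP wording and one simulation. The statistical cost, at assumed adverse-event rates of 30% v 10%:

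| Chance of | Flat 0.90 | Illustrative thresholds |
|---|---|---|
| Adverse-event clause met by second look | 88% | 52% |
| Adverse-event clause met by the end | 96% | 81% |
| Full rule selects COpAT, 90% cure | 34-36% | 28-29% |
| Full rule selects COpAT, 95% cure | 72-77% | 60-63% |

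Early stops would be fewer.

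### The early stopping rule selects COpAT at the interim crossing, and nothing brings randomised patients still in follow-up into that selection or says which result governs if they disagree

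*Combined protocol and SAP*

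**What the plan says.** The rule is in the Statistical Analysis Plan, under Early Stopping and Selection. It defines the adverse-event quantities ("Denoting the posterior probabilities of adverse event outcome p_1 (Control Arm) and p_2 (Experimental Arm), respectively") and the efficacy quantities ("the posterior probabilities of efficacy outcome by q_1 (Control Arm) and q_2 (Experimental Arm), respectively"). It requires Prob{p1 > p2 | data} > 0.90 and Prob{|q1 - q2| < 0.10 | data} > 0.90. If both hold, "then the trial will be stopped early, and the experimental arm will be selected as superior arm".

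The same paragraph says that "the predictive probability (for the final sample size) of primary outcomes will be estimated, given the current data", but this predictive probability does not appear in the rule, which conditions on current data only.

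Data Safety Monitoring places the looks "after 45 patients are enrolled, after 90 patients are enrolled, and after 135 patients are enrolled", so enrolment triggers them, not completed follow-up. Objectives sets both primary outcomes at 3 months. The Research Summary, under Study Duration, gives the timetable: "Enrollment is expected to take up to 4 months to achieve the proposed sample size. Subjects will be followed for 3 months after hospital discharge". Section II repeats it and adds that the final analysis takes place when the study concludes. Neither place links that analysis to an early stop.

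**The concern.** An interim crossing can be a reason to stop enrolling, or it can be the trial's conclusion. This rule makes it both. A patient who has been randomised but has not reached 3 months contributes nothing to the selection, although that patient's outcome will be known within weeks at no extra cost.

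The plan does not require the rule to be checked again once those outcomes are in. It also does not say whether the interim or the completed result is the trial's result if they differ. At stake is a claim of superior safety with equivalent cure that rests on part of the randomised population and may not hold in all of it. The plan itself says that 135 patients are needed.

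**Working it through.** **The plan's own figure.** The only stated figure is that 135 patients (90 and 45) give power above 80%. It cannot be reproduced, because no rates or alpha are given. As orientation, 45 v 90 patients give 81% power for adverse events of 30% v 10% at two-sided 0.05, so that pair serves as the real-effect scenario below.

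**Who is pending at each look** (even accrual, follow-up counted from enrolment). Patients with complete outcomes at time t = accrual rate × (t − 3 months).

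- Planned 4 months: 135/4 = 33.75 a month. Look 1 is at 45/33.75 = 1.33 months and look 2 at 90/33.75 = 2.67 months. Both come before 3 months, so none are complete and 45 or 90 are pending. Look 3 is at 4.0 months: 33.75 × 1 ≈ 34 complete, 101 pending.
- Slower accrual, 12 months (assumed): 135/12 = 11.25 a month. Look 2 is at 8.0 months: 11.25 × 5 ≈ 56 complete, 34 pending.

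On either timetable, randomised patients are outstanding at every look.

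**Can pending patients undo the decision?** Take look 2 of the 12-month case, with 19 control and 37 experimental complete, 11 and 23 pending, and Beta(1,1) priors.

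- Interim: adverse events 6/19 v 5/37 give Prob{p1 > p2} = 0.944. Cure 19/19 v 36/37 gives Prob{|q1 − q2| < 0.10} = 0.917. The rule is met.
- If the pending patients' cure is 11/11 v 20/23, the totals are 30/30 v 56/60 and the efficacy probability is 0.875.
- If their adverse events are 1/11 v 3/23, the totals are 7/30 v 8/60 and the safety probability is 0.889.

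Either outcome takes the rule below 0.90. In 20,000 simulated trials of this case with adverse events 20% in both arms and cure 95%, 358 met the rule and 193 of those (54%) no longer met it after the 34 were added; 193/20,000 = 1.0% of all trials. With adverse events 30% v 15% and cure 95%, it was 440 of 1,737 (25%), and 440/20,000 = 2.2% of all trials.

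**How often, if looks use complete outcomes at 45, 90 and 135.** The assumptions are cumulative control:experimental numbers of 15:30, 30:60 and 45:90, all 135 already randomised, and 400,000 simulated trials per scenario. The table shows trials that meet the rule at 45 or 90 and no longer meet it at 135.

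| Adverse events (control v experimental), cure | Prior | Share of stops | Share of all trials |
|---|---|---|---|
| 20% v 20%, 95% | uniform | about 46% | 1.9% |
| 20% v 20%, 98% | uniform | 42% | 3.3% |
| 20% v 20%, 95% | Jeffreys | 55% | 3.7% |
| 20% v 20%, 98% | Jeffreys | 55% | 6.9% |
| 30% v 10%, 95% | uniform | about 9% | 3.0% |
| 30% v 10%, 95% | Jeffreys | 10% | 4.6% |

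The last column is the third multiplied by the chance of stopping. That chance is about 4-13% in the equal-rate rows and 34-46% in the 30% v 10% rows (for example, 46% × 10% = 4.6%).

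**The first look.** With uniform priors, 15 v 30 patients and every patient cured, the efficacy probability is 0.87, its maximum. The rule cannot be met at 45, so every uniform-prior stop in the table is at 90. With Jeffreys priors a stop at 45 is possible.

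**The case against.** The strongest reply is that the plan follows every subject for 3 months and performs a final analysis at the study's conclusion, so nobody is lost. This stands in part. A reader might infer that pending patients are discarded, and the documents do not say so. But those general statements do not bring the patients into the selection, do not call for the rule to be rechecked, and do not say which result prevails.

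A reader might also infer that an early stop spares no one and gains no time, because on a 4-month accrual the first 45 and 90 complete outcomes arrive at months 4.33 and 5.67 (1.33 + 3 and 2.67 + 3), after enrolment has closed. That holds only if the looks are moved to completed outcomes. The plan triggers them by enrolment, so a stop at 45 or 90 would leave 90 or 45 patients unrandomised. For the same reason, it cannot be said that 90 randomised patients would be omitted at the first look. On the planned timetable the difficulty at looks 1 and 2 is that no 3-month outcomes exist, which is a separate question.

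Two further points stand. The high percentages are conditional on stopping, and as a share of all trials they are small. Some slippage after crossing a boundary occurs in any sequential design. Neither removes the need to say which result governs.

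**Conclusion.** The concern holds as a gap in the decision rule. Selection is tied to the interim crossing, randomised patients still in follow-up are not part of it, and no text says which result governs if the completed data differ.

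The size is moderate. If the adverse-event rates are truly equal, roughly half of early stops would not meet the rule in all 135 (42-46% with uniform priors, 55% with Jeffreys), but this is only 2-7% of all trials. With a real effect of 30% v 10% and cure at 95%, about nine stops in ten survive. These figures rest on assumed rates, priors and complete outcomes at each look, since the plan states neither rates nor a prior.

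No longer meeting the rule means that one probability has fallen to 0.90 or below. A reader might take it to mean that control is better, and the calculation does not show that.

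**What to change.** Replace the action in Early Stopping and Selection with wording such as:

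*If the rule is met, enrolment stops; all randomised patients complete the planned 3-month follow-up; the experimental arm is selected only if the same two criteria (Prob{p1 > p2 | data} > 0.90 and Prob{|q1 − q2| < 0.10 | data} > 0.90) hold in all randomised patients; this analysis is primary and the interim result is supportive.*

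The two criteria are restated because the plan defines no separate final criterion. The change adds no patients or visits.

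It has two costs. The conclusion waits up to about 3 months for follow-up already planned. A small share of trials with a true effect that cross at an interim would not be declared a success: about 3-5% of all trials at 30% v 10% and cure 95%, under the assumptions above.
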